8.2 Safety Assessments

This section presents safety assessments other than AEs, which are presented in Section 8.3.

Planned time points for all safety assessments are provided in the SoA (Section 1.2).

8.2.1 Medical History

Prior to enrollment, participants will be assessed for pre-existing conditions and illnesses, both past and ongoing. Any such conditions will be documented in the source document. Significant (clinically relevant) medical history (reported as diagnosis) including conditions/illnesses for which the participant is or has been followed by a physician or conditions/illnesses that could resume during the course of the study or lead to an SAE/AESI or to a repetitive outpatient care will be collected in the CRF. Collected information will not be coded.

8.2.2 Physical Examinations

At Visit 01, the Investigator or a designee will perform a history-directed physical examination. Information will be recorded in the source document.

8.2.3 Vital Signs

Oral (participants 3 years to < 9 years and participants \geq 65 years of age) or rectal (participants 6 months to < 36 months) pre-vaccination temperature will be assessed by the investigator prior to immunization. Tympanic, skin, and temporal artery thermometers must not be used.

8.2.4 Clinical Safety Laboratory Assessments

Not applicable.

8.3 Adverse Events (AEs), Serious Adverse Events, and Other Safety Reporting

The definitions of an AE, SAE, and the different categories of AEs can be found in Appendix 10.2.

AEs will be reported by the participants or participants' parents/legally acceptable representatives to the investigator, then by the investigator to the Sponsor.

The investigator and any qualified designees are responsible for detecting, documenting, and recording events that meet the definition of an SAE/AESI and remain responsible for following up AEs that are serious, considered related to the study intervention or study procedures, or that caused the participant to discontinue the study (see Section 7).

The method of recording, evaluating, and assessing causality of AEs and SAEs and the procedures for completing and transmitting SAE reports are provided in Appendix 10.2.

8.3.1 Time Period and Frequency for Collecting AE and SAE Information

Immediate Post-vaccination Observation Period

Participants will be kept under observation for 20 minutes after each vaccination to ensure their safety. The post-vaccination observation should be documented in the source document.

Adverse Events of Special Interest

Adverse events of special interest will be collected from Visit 1 to Visit 2 for participants receiving 1 dose of study vaccine, and from Visit 1 to Visit 3 for participants receiving 2 doses of study vaccine.

AESIs will be captured as SAEs. See Section 8.3.6 for the list of AESIs.

SAEs

Information on SAEs will be collected and assessed throughout the study, from Visit 1 to Visit 2 for participants receiving 1 dose of study vaccine, and from Visit 2 to Visit 3 for participants receiving 2 doses of study vaccine. However, before the first study intervention administration, only SAEs related to study procedures are to be collected in the CRF (e.g., SAEs related to blood sampling).

All SAEs will be recorded and reported to the Sponsor or designee immediately and under no circumstance should this exceed 24 hours, as indicated in Appendix 10.2. The investigator will submit any updated SAE data to the Sponsor within 24 hours of it being available.

Investigators are not obligated to actively seek information on AEs or SAEs after conclusion of the study participation. However, if the investigator learns of any SAE, including a death, at any time after a participant has been discharged from the study, and he/she considers the event to be reasonably related to the study intervention or study participation, the investigator must promptly notify the Sponsor.

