1.2 Schedule of Activities (SoA)

Visit procedures are detailed in the Operating Guidelines.

. . .

Table 1.2: Schedule of activities 1

п п

...

() ()

For Participants 6 Months to < 9 Years of Age: Phase IV Study, 2 or 3 Visits, 1 or 2 Vaccinations, 1 or 2 Telephone Calls, 2 Blood Samples, 1 or 2 Month	IS
Duration Per Participant	

ъ

	All Participants			Participants Receiving 1 Dose of Influenza Vaccine	Participants Receiving 2 Doses of Influenza Vaccine		
Visit/Contact	Collection	Visit 1	Telephone Contact	Visit 2	Visit 2	Telephone Contact	Visit 3
Study timelines (days)	of information in the CRF	Day 01	Visit 1 + 21 days	Visit 1 + 28 days	Visit 1 + 28 days	Visit 2 + 21 days	Visit 2 + 28 days
Time windows (days)		-	+ 19 to 23 days	+ 28 to 35 days	+ 28 to 35 days	+ 19 to 23 days	+ 28 to 35 days
Visit procedures:							
Informed consent/assent ^a	Х	Х					
Inclusion/exclusion criteria	Х	Х					
Collection of demographic data	Х	Х					
Collection of medical history	Х	Х					
Influenza vaccination history	Х	Х					
History-directed physical examination		Х			Х		
Pre-vaccination temperature ^b	Х	Х			Х		
Review contraindications for vaccination	Х				Х		
Allocation of participant number	Х	Х					
Blood sampling (BL) ^c	Х	BL0001		BL0002A			BL0002B
Vaccination ^d	Х	X			Х		
Immediate surveillance (20 minutes)	Х	X			Х		
Diary card (DC) provided		DC1			DC2		
Telephone contact ^e			Х			X	

Sanofi Pasteur 450–Fluzone[®] Quadrivalent, 522–Fluzone[®] High-Dose Quadrivalent

	A	All Participants Receiving 1 Dose Influenza Vacci			Participants Receiving 2 Doses of Influenza Vaccine		
Visit/Contact	Collection	Visit 1 Telephone Visit 2		Visit 2	Visit 2	Telephone Contact	Visit 3
Study timelines (days)	of information in the CRF	Day 01	Visit 1 + 21 days	Visit 1 + 28 days	Visit 1 + 28 days	Visit 2 + 21 days	Visit 2 + 28 days
Time windows (days)		-	+ 19 to 23 days	+ 28 to 35 days	+ 28 to 35 days	+ 19 to 23 days	+ 28 to 35 days
Diary card reviewed				DC1	DC1		DC2
Diary card collected				DC1	DC1		DC2
Interim history	Х			Х	Х		Х
Reporting medical events to allow for the collection of SAEs and AESIs	Х			To be reported throughou	t the study perio	d	
Collection of reportable concomitant medications	Х	X		Х	X		X
End of Active Phase participation record ^f	Х			Х			Х

AESI: adverse event of special interest; CRF: case report form; SAE: serious adverse event

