- ^a Informed consent form will be signed and dated by parent(s) or guardian(s) for participants 6 months to < 9 years of age and assent form will be signed and dated by participants 7 to < 9 years of age.
- ^b The preferred route for this study is rectal for participants 6 to < 36 months of age, and oral for participants 3 to < 9 years of age. The axillary route may be used when a rectal or oral temperature cannot be obtained.
- ^c A blood sample, approximately 5 mL, will be collected from all participants at Visit 1, prior to vaccination, and at either Visit 2 (for participants receiving 1 influenza vaccine dose) or at Visit 3 (for participants receiving 2 influenza vaccine dose).
- ^d One or 2 doses of influenza vaccine will be administered according to the ACIP guidance in effect during the study. If 2 doses of influenza vaccine are indicated, 1 dose will be administered during Visit 1 and the second dose will be administered approximately 28 days later during Visit 2.
- ^e The participant's parent/guardian will be contacted by telephone 21 (window, 19–23) days after vaccination as a reminder to notify the site immediately if a serious medical event (e.g., hospital visit) occurs and to complete the diary card and to bring it with them to the next visit.
- ^f The End of Active Phase participation record will be completed at Visit 2 for participants receiving 1 dose of influenza vaccine or at Visit 3 for participants receiving 2 doses of influenza vaccine. In case of participant discontinuation at a visit, the entire visit will be completed.

Table 1.3: Schedule of activities 2.

For Participants ≥ 65 Years of Age: 2 Visits, 1 Vaccination, 1 Telephone Call, 2 Blood Samples, 21 Days Duration Per Participant

Visit/Contact	Collection	Visit 1	Telephone Contact ^c	Visit 2
Study timelines (days)	of information in the CRF	Day 01	Visit 1 + 14 days	Visit 1 + 21 days
Time windows (days)		-	+ 12 to 16 days	+ 21 to 28 days
Visit procedures:				
Informed consent	Х	Х		
Inclusion/exclusion criteria	Х	Х		
Collection of demographic data	Х	Х		
Collection of medical history	Х	Х		
Influenza vaccination history (previous season)	Х	Х		
History-directed physical examination		Х		
Pre-vaccination temperature ^a	Х	Х		
Allocation of participant number	Х	Х		
Blood sampling (BL) ^b	Х	BL0001		BL0002
Vaccination	Х	Х		
Immediate surveillance (20 minutes)	Х	Х		
Diary card provided		Х		
Telephone contact ^c			Х	

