6.8 Concomitant Therapy

Reportable medications include medications that may affect the interpretation of safety data or may interfere with the development or measurement of the immune response (e.g., the use of immune-suppressors, immune-modulators, or some antibiotics that can affect certain bioassays). Some medications such as steroids can affect both the evaluation of the safety and the immune response to a vaccine.

This may include medications of interest that were started prior to the day of vaccination, and even stopped prior to enrollment if there is a reasonable possibility that they may have an impact on safety and / or immune assessment during study participation.

The following reportable medications are defined:

- Category 2: medications impacting or that may have an impact on the immune response (eg, other vaccines, blood products, antibiotic classes that may interfere with bioassays used by Sanofi Pasteur laboratory or other testing laboratories, systemic steroids/corticosteroids, immune-suppressors, immune-modulators with immunosuppressive properties, anti-proliferative drugs such as DNA synthesis inhibitors
- Category 3: medications impacting or that may have an impact on both the safety and the immune response (eg, systemic steroids/corticosteroids)

Reportable medications will be collected in the CRF from the day of each vaccination to the end of the follow-up period (i.e., from Visit 1 through Visit 2 for participants receiving 1 dose of study vaccine or from Visit 1 through Visit 3 for participants receiving 2 doses of study vaccine).

Dosage and administration route, homeopathic medication, topical and inhaled steroids, as well as topical, ophthalmic, and ear treatments will not be recorded.

Topical analgesics should not be applied at the site of vaccination; however, if they are applied inadvertently to the vaccination site, they should be recorded as a Category 3 medication.

Medications given in response to an AE will be captured in the "Action Taken" section of the AE CRF only. No details will be recorded in the concomitant medication Form of the CRF unless the medication(s) received belongs to one of the pre-listed categories. Medications will not be coded.

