8.3.6 Adverse Events of Special Interest

Adverse events of special interest will be captured as SAEs. These include new onset of GBS, encephalitis/myelitis (including transverse myelitis), neuritis (including Bell's palsy, optic neuritis, and brachial neuritis), thrombocytopenia, vasculitis, convulsions (including febrile convulsions [children only]), and anaphylaxis or other hypersensitivity/allergic reactions from Visit 1 through Visit 2 for participants receiving 1 dose of vaccine, or from Visit 1 through Visit 3 for participants receiving 2 doses of vaccine.

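### Section 8.3.1 starts the SAE collection window for two-dose children at Visit 2, although dose 1 is given at Visit 1 and the rest of the protocol collects from Visit 1

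*Combined protocol and SAP*

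**What the plan says.** The SAE paragraph of section 8.3.1 opens with "Information on SAEs will be collected and assessed throughout the study". It then gives Visit 1 to Visit 2 for one-dose participants, "and from Visit 2 to Visit 3 for participants receiving 2 doses of study vaccine". Its next sentence restricts what is recorded before the first study vaccination to SAEs caused by study procedures.

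The other statements on timing are:

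- **Dosing (Table 1.2, footnote d):** where two doses are indicated, "1 dose will be administered during Visit 1 and the second dose will be administered approximately 28 days later during Visit 2".
- **AESIs (section 8.3.1, preceding paragraph):** "from Visit 1 to Visit 3 for participants receiving 2 doses of study vaccine". The same paragraph says that AESIs are captured as SAEs.
- **AESIs again (section 8.3.6):** "or from Visit 1 through Visit 3 for participants receiving 2 doses of vaccine".
- **Schedule of activities (Table 1.2):** the row "Reporting medical events to allow for the collection of SAEs and AESIs" carries one entry, which applies to the whole study period.
- **Reportable medications (section 6.8):** "or from Visit 1 through Visit 3 for participants receiving 2 doses of study vaccine".

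**The concern.** Section 8.3.1 is where the protocol defines the period for collecting safety information, and it is the only place that gives a visit-to-visit window for SAEs. Taken at its word, that window opens only when the second dose is due. A two-dose child admitted to hospital ten days after dose 1, for something not on the AESI list, would fall outside it.

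The study has no endpoints, so SAEs and AESIs are the only participant outcomes that section 9.4 reports. Section 9.4.5 promises listings or tables of them without stating a period. Section 9.4 says that no separate SAP will be written, so no later document is planned that would settle the window. The analysis set in section 9.3 starts at the first dose, while the literal SAE window starts at the second. An SAE after dose 1 could therefore be missing from the CRF and the listing for a child who is in the analysis set.

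**Working it through.** The plan states no figure to reproduce. The check is a comparison of the text, followed by the length of the gap.

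**Comparison for a two-dose child**

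| Place | Period stated or implied | Agrees with a Visit 2 start? |
|---|---|---|
| 8.3.1, SAEs, opening clause | Whole study | No |
| 8.3.1, SAEs, two-dose clause | Visit 2 to Visit 3 | This is the disputed clause |
| 8.3.1, SAEs, next sentence | Limits recording before dose 1, so presumes collection from Visit 1 | No |
| 8.3.1 and 8.3.6, AESIs | Visit 1 to Visit 3, captured as SAEs | No |
| Table 1.2, SAE and AESI row | Whole study period | No |
| 6.8, reportable medications | Visit 1 through Visit 3 | Different data item; supporting evidence only |

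The AESI rows are a direct conflict. An AESI on Day 10 is inside the AESI window and must be captured as an SAE, yet it is outside the SAE window. Because the AESI rule covers such events in its own right, the events left exposed are SAEs that are not AESIs.

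**Length of the gap**

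Inputs, from the Synopsis and Table 1.2:

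- Visit 1 to Visit 2 = a = 28 days (window 28 to 35)
- Visit 2 to Visit 3 = b = 28 days (window 28 to 35)

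Total follow-up = a + b, which runs from 28 + 28 = 56 to 35 + 35 = 70 days.

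Share outside the literal window = a / (a + b):

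- Nominal: 28 / (28 + 28) = 28/56 = 50.0%
- Smallest: 28 / (28 + 35) = 28/63 = 44.4%
- Largest: 35 / (35 + 28) = 35/63 = 55.6%

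**Children affected**

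Groups 1 and 2 are planned at about 30 each, so at most 30 + 30 = 60 of the 90 participants could receive two doses. The documents do not say how many will, so the range is 0 to 60. They give no SAE rate either, so a number of missed events cannot be projected.

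**The case against.** The strongest reply is that this is a drafting slip which the rest of the protocol overrides:

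- Section 8 makes adherence to the schedule of activities mandatory, and Table 1.2 covers the whole study.
- Section 8.3 makes the investigator responsible for detecting and recording SAEs, with no visit limit. The paragraph after the disputed sentence requires all SAEs to be reported within 24 hours.
- The telephone contact 21 days after dose 1 serves "as a reminder to notify the site immediately if a serious medical event (e.g., hospital visit) occurs". At Visit 2 the first diary card is reviewed, an interim history is taken and contraindications are checked. Section 8.3.2 requires information gathered by the site to be entered in the web-based CRF.
- The study is descriptive, and its objective is to supply serum.

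Most of this stands. It makes substantial loss of events unlikely at sites that work from Table 1.2. It is also fair that the medication window in section 6.8 only corroborates, and that nothing in the documents shows sites or the CRF using the literal window. The CRF specification and the Operating Guidelines are not available to check.

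The objection does not rescue the clause. A site cannot follow both Table 1.2 and the Visit 2 start, and anyone setting up the CRF or the listing would look to section 8.3.1 for the window.

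**Conclusion.** The concern holds. The two-dose clause in section 8.3.1 is wrong as written: it contradicts its own sentence, the next sentence, the AESI rules and Table 1.2. The weight of the text shows that collection from Visit 1 is intended, so this is an internal contradiction and not a deliberate plan to skip the interval.

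Read literally, 28 to 35 of 56 to 70 days per two-dose child (50% nominal, 44% to 56% across the windows) fall outside SAE collection, for SAEs that are not AESIs. These percentages describe the period excluded by the text, not expected data loss. They assume that visits take place within their stated windows. The practical risk is under-capture, which could differ between sites if some work from section 8.3.1 and others from Table 1.2.

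The clause should be corrected because it is an operative safety-collection rule. No hypothesis test, power calculation or sample size depends on it.

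**What to change.** In the SAE paragraph of section 8.3.1, change the start of the two-dose window from Visit 2 to Visit 1, so that it matches the AESI paragraph: "from Visit 1 to Visit 3 for participants receiving 2 doses of study vaccine". This reconciles it with section 8.3.6 and Table 1.2, and brings it into line with section 6.8. Then confirm that the CRF, the Operating Guidelines and the specification of the section 9.4.5 SAE listing use the same window.

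The cost is one visit number in one sentence and a check of those documents. It adds no visit, procedure, blood sample or participant.

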8.3.2 Method of Detecting SAEs/AESIs

Individual diary cards, specifically designed for this study by the Sponsor and provided to the study sites, will be given to study participants for the recording of daily safety information. These diary cards will include areas for free text to capture additional safety information or other relevant details.

At specified intervals, the Investigator or a designee will interview the participants or participants' parents/legally acceptable representatives to collect the information recorded in the diary card, and will attempt to clarify anything that is incomplete or unclear. All clinical study information gathered by the study site will be reported electronically by the Investigator or designee using a web-based CRF. Any information that was not documented in the diary card will first be captured in the source document and then reported electronically.

Care will be taken not to introduce bias when detecting SAEs/AESIs. Open-ended and non-leading verbal questioning of the participant is the preferred method to inquire about SAE occurrences.

8.3.3 Follow-up of SAEs and AESIs

After the initial SAE/AESI report, the investigator is required to proactively follow each participant at subsequent visits/contacts, unless a participant or participant's parents/legally acceptable representative(s) refuses further contact. All AEs that are considered by the Investigator as serious, or related to the study intervention administered, or that led to study or vaccination discontinuation, or AESIs (as defined in Section 8.3.6)], will be followed during the conduct of the study until resolution, stabilization, or the participant is lost to follow-up (as defined in Section 7.3). For related SAEs ongoing at last study visit, such follow-up may need to continue after the end of the study.

Further information on follow-up procedures is provided in Appendix 10.2.

8.3.4 Regulatory Reporting Requirements for SAEs

- Prompt notification by the investigator to the Sponsor of an SAE is essential so that legal obligations and ethical responsibilities towards the safety of participants and the safety of a study intervention under clinical investigation are met.
- The Sponsor has a legal responsibility to notify both the local regulatory authority and other regulatory agencies about the safety of a study intervention under clinical investigation. The Sponsor will comply with country-specific regulatory requirements relating to safety reporting to the regulatory authority, Institutional Review Boards (IRB)/Independent Ethics Committees (IEC), and investigators.
- An investigator who receives an investigator safety report describing a SAE or other specific safety information (eg, summary or listing of SAEs) from the Sponsor will review and then file it and will notify the IRB/IEC, if appropriate according to local requirements.

• Investigator safety reports must be prepared for suspected unexpected serious adverse reactions (SUSAR) according to local regulatory requirements and Sponsor policy and forwarded to investigators as necessary.

8.3.5 Pregnancy

Not applicable as the study does not include women of childbearing potential.

8.3.6 Adverse Events of Special Interest

Adverse events of special interest will be captured as SAEs. These include new onset of GBS, encephalitis/myelitis (including transverse myelitis), neuritis (including Bell's palsy, optic neuritis, and brachial neuritis), thrombocytopenia, vasculitis, convulsions (including febrile convulsions [children only]), and anaphylaxis or other hypersensitivity/allergic reactions from Visit 1 through Visit 2 for participants receiving 1 dose of vaccine, or from Visit 1 through Visit 3 for participants receiving 2 doses of vaccine.

8.4 Pharmacokinetics

Pharmacokinetic parameters are not evaluated in this study.

8.5 Genetics

Genetics are not evaluated in this study.

8.6 Biomarkers

Biomarkers are not evaluated in this study.

8.7 Immunogenicity Assessments

See Section 8.1.2.

8.8 Medical Resource Utilization and Health Economics

Medical Resource Utilization and Health Economics parameters are not evaluated in this study.

8.9 Leftover Biological Samples and Use of Data

Any unused part of the biological samples collected for this study (serum samples) are being retained in long-term storage to support answers to regulatory questions related to the product's licensure and the potential revalidation of the study results.

In addition, participants or participants' parents/legally acceptable representatives will be asked to indicate in the ICF whether they will permit the future use of any unused stored biological samples for other tests, unless prohibited by local laws or IRBs/IECs (in such case, consent for future use of any unused biological samples will not be included in the site-specific ICF). If they refuse permission, the biological samples will not be used for any testing other than that directly related to this study. If they agree to this future use, they will not be paid for giving permission. The aim of any possible future research is unknown today, and may not be related to this particular study. It may be to improve the knowledge of vaccines and their mechanism of action, the knowledge of infectious diseases, or to improve existing tests or develop new tests to assess vaccines, or to help identify new vaccine targets or biomarkers that predict participant response to the vaccine. Such research may also include, but is not limited to, performing assessments on DNA, RNA, proteins or metabolites. If future research on genetic material is performed, a specific individual consent will be obtained.

Data and samples will be used in compliance with the information provided to participants in the ICF Part 2 (future research). In the event future research is conducted for other purposes, the study participants will be informed of those purposes and will be given means to object to the use of their biological samples or data for those research projects.

All study participant data and biological samples will be coded such that no direct identifiers will be linked to participants. Coded data and biological samples may be transferred to a Sponsor site (or a subcontractor site), which may be located outside of the country where the study is conducted. The Sponsor adopts safeguards for protecting participant confidentiality and personal data (see Section 10.1.4).

The biological samples will be securely stored at the Sanofi Pasteur laboratory and/or other laboratories for up to 25 years after the end of the study. Any samples remaining at the end of retention period will be destroyed. If a participant requests destruction of his/her samples before the end of the retention period, the Investigator must notify the Sponsor (or its contract organization) in writing. In such case, samples will be destroyed and sample related coded data will be anonymized unless otherwise required by applicable laws.

Study participant coded data will be stored for future research for up to 25 years after the end of the study. If data are still considered of important scientific value after this period, coded data already available will be anonymized unless otherwise required by applicable laws (the same will apply to the data of a study participant who has requested the destruction of his/her samples).

Participant's coded data sets provided to researchers for a specific research project will be available to the researchers for a maximum of 2 years after the end of their specific project (end of project is defined by publication of the results or finalization of the future research project report).

Note: The other biological samples collected to qualify the participant for inclusion in the study or to monitor his/her health during the study are dedicated for immediate use. If any of these biological samples are not completely used up, they will be destroyed at the latest at the end of the study or after the time requested by local law.

9 Statistical Considerations

